#### **4.2.7.3 Primary Analysis of Secondary Endpoint**

Only participants with measurable disease at baseline are included in summaries of change in tumour size (measurable disease is as denoted on the eCRF by the investigator).

The TL tumour size and percentage change in TL tumour size from baseline is summarised using descriptive statistics and presented at each timepoint.

The median best percentage change from baseline and other summary statistics are presented, together with the number of participants. The median percentage change from baseline at each post baseline assessment timepoint and other summary statistics are presented, together with the number of participants.

The best percentage change from baseline in tumour size is presented graphically using waterfall plots, with the bars ordered from the largest increase to the largest decrease. Separate waterfall plots are used to present each participant's best percentage change in TL tumour size as a separate bar. A reference line at the -30% change in TL tumour size level is added to the plots, which corresponds with the definition of 'partial response'. All progressions are marked with a '●' or designated with patterns or colors for ORR categories. Flagged progressions on the percentage change in TL tumour size at a particular timepoint are based upon NTL or new lesion progression at that timepoint and flagged progressions on the best percentage change will be based upon NTL or new lesion progression at the same timepoint as the best percentage change. The scale in these plots are fixed to be from -100 to 100 to avoid presenting extreme values. Values that are capped as a result of this restriction to the scale are marked with '#'. Values are ordered in descending order with the imputations due to death appearing first followed by a gap followed by all other participants.

Additionally, ‘spider’ plots of percentage change from baseline in TL size by participant are presented. This depicts each participant’s percentage change from baseline in TL tumour size as a line over time and progression due to non-target and/or new lesions are indicated.

#### **4.2.8 Secondary Endpoint: Overall Survival**

Overall Survival (OS) is a secondary efficacy endpoint.

##### **4.2.8.1 Definition**

Overall survival is defined as the time from the date of first IP dose until death due to any cause regardless of whether the participant withdraws from study therapy or receives another anti-cancer therapy.

##### **4.2.8.2 Derivations**

$$\text{OS (Months)} = \frac{(\text{Date of death or censoring-date of first dose of IP})+1}{(\frac{365.25}{12})}$$

Any participant not known to have died at the time of analysis is censored based on the last recorded date on which the participant was known to be alive.

Note: For any OS analysis performed (prior to the final OS analysis), in the absence of survival calls being made, it may be necessary to use all relevant eCRF fields to determine the last recorded date on which the participant was known to be alive for those participants still on treatment (since the SURVIVE module is only completed for participants off treatment if a survival sweep is not performed). The last date for each individual participant is defined as the latest among the following dates recorded on the eCRFs:

- AE start, stop and change in severity dates
- Admission and discharge dates of hospitalization
- Physical examination, ECOG and ECG dates
- IP Treatment administration dates
- End of treatment date
- Concomitant medication start and stop dates
- Laboratory test dates
- Date of vital signs
- Disease assessment dates on RECIST v1.1 eCRF

- Start and stop dates of alternative anticancer treatment
- Date last known alive on survival status eCRF
- End of study date

The proportion of participants alive at 3, 6, 9 and 12 months (OS-3, OS-6, OS-9, OS12) is defined as the Kaplan-Meier estimate of OS at 3, 6, 9, and 12 months.

Duration of follow-up for OS is reported separately for censored participants and non-censored participants and is defined as follows:

Duration of follow up for OS (Months) =

$$\frac{(\text{Date of death or censoring (date last known to be alive)} - \text{date of first dose of IP}) + 1}{(\frac{365.25}{12})}$$

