7.3 Lost to Follow-Up

A participant will be considered lost to follow-up if he or she repeatedly fails to return for scheduled visits and is unable to be contacted by the study site.

The following actions must be taken if a participant fails to return to the clinic for a required study visit:

- The site must attempt to contact the participant and reschedule the missed visit as soon as possible and counsel the participant on the importance of maintaining the assigned visit schedule and ascertain whether or not the participant wishes to and/or should continue in the study.
- Before a participant is deemed lost to follow-up, the Investigator or designee must make every effort to regain contact with the participant (where possible, 3 telephone calls and, if necessary, a certified letter to the participant's last known mailing address or local equivalent methods). These contact attempts should be documented in the participant's medical record.
- Should the participant continue to be unreachable, he/she will be considered to have withdrawn from the study.

Discontinuation of specific sites or of the study as a whole are handled as described in Appendix A.

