8.2.8 Survival Follow-up

All participants will be followed for survival until death, lost to follow-up, withdrawal of consent, or end of study whichever occurs first. Participants will be followed for survival by telephone calls, email, or clinic visits approximately every 12 weeks. During this period, information will be collected in the eCRF on survival status and any new anti-cancer therapies, and on any SAEs considered related to study intervention or study procedures.

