The DCR at 15 weeks is defined as the percentage of participants who have a BoR of CR or PR in the first 16 weeks (to allow for late assessment within the assessment window) or who have SD for at least 14 weeks after the start of treatment (to allow for early assessment within the assessment window). The DCR and its 90% CIs (Clopper Pearson method; Clopper et al, 1934) will be summarised.

Percentage Change in Tumour Size

The percentage change in TL tumour size from baseline will be summarised using descriptive statistics by timepoint. Best percentage change will also be summarised.

Waterfall plots showing the percentage change at 15 weeks and the best percentage change from baseline in sum of the diameters of TLs will be produced. Spider plots showing the percentage change from baseline in tumour size for each participant over time will be produced.

Progression-free Survival

The PFS is defined as the time from the start of study intervention until the date of objective disease progression or death (by any cause in the absence of progression), regardless of whether the participant withdraws from study intervention or receives another anti-cancer therapy prior to progression. Participants who have not progressed or died at the time of analysis will be censored at the time of the latest date of assessment from their last evaluable RECIST assessment.

The PFS time will always be derived, based on scan/assessment dates, not visit dates.

The RECIST assessments/scans contributing towards a particular visit may be performed on different dates. The following rules will be applied:

- Date of progression will be determined, based on the earliest of the dates of the component that triggered the progression.
- When censoring participants for PFS, the participant will be censored at the latest of the dates contributing to a particular overall visit assessment.

Progression-free survival will be summarised descriptively, and Kaplan-Meier plots will be provided.

Overall Survival

Overall survival is defined as the time from the start of treatment until death due to any cause. Any participant not known to have died at the time of analysis will be censored based on the last recorded date on which the participant was known to be alive.

Overall survival will be summarised descriptively, and Kaplan-Meier plots will be provided.

Change in ctDNA

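### SAP 4.2.8.2 lets an undefined end-of-study date set the last-known-alive date for OS, so survival can be credited beyond the last contact

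*SAP*

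**What the plan says.** Protocol 9.4.3 censors participants not known to have died "based on the last recorded date on which the participant was known to be alive". SAP 4.2.8.2 repeats that rule. A Note then deals with how to find the date: "For any OS analysis performed (prior to the final OS analysis), in the absence of survival calls being made", all relevant eCRF fields may be needed for participants still on treatment, because the survival form is completed only off treatment unless a survival sweep is done.

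The next sentence is worded more widely: "The last date for each individual participant is defined as the latest among the following dates recorded on the eCRFs". Twelve kinds of date follow. The eleventh is the last-alive date on the survival-status form; the twelfth is "End of study date".

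On follow-up, protocol 8.2.8 states: "Participants will be followed for survival by telephone calls, email, or clinic visits approximately every 12 weeks". Protocol 7.3, after describing missed visits and repeated contact attempts, states: "Should the participant continue to be unreachable, he/she will be considered to have withdrawn from the study". Protocol 7.2 adds that participants are withdrawn if the Sponsor terminates the study.

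**The concern.** The rule and its implementation can disagree. The rule asks when someone last knew the participant was alive. The list takes a maximum over dates, one of which may only record when the participant's file was closed. If that date comes after the last contact, the maximum selects it over the survival-status date.

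The participant then stays in the risk set over a period when a death would not have been seen. At each death time the Kaplan-Meier factor should be 1 − d/(n − k), with d deaths, n nominally at risk and k participants carried past their last contact. The derivation gives 1 − d/n, which is larger. The error therefore runs one way. It reaches the OS median, the 3-, 6-, 9- and 12-month rates and the OS follow-up summaries.

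Deaths may be affected too. SAP 4.2.8.3 imputes a partial death date as the later of the day after the last known alive date and the first of the recorded month or year. It censors at the last known alive date when the death date is wholly missing. If the same derivation supplies that date, an end-of-study entry made when a site learns of a death could push the imputed death later, or count a person as alive past death.

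**Working it through.** **1. Plan's own figure.** There is none. Neither document gives an assumed OS, an event count or a loss-to-follow-up rate, so nothing can be reproduced.

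**2. Whom the item affects.** Read within the Note's limits (before the final analysis, still on treatment), the item does almost nothing, because a participant still on treatment would not ordinarily have an end-of-study date. It has effect mainly for those who have left the study. The operative sentence covers each participant, the list includes subsequent anticancer therapy and survival-status dates, and the SAP gives no other derivation of the last-known-alive date. A programmer could reasonably apply it to everyone.

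**3. Can the date fall after the last alive contact?** Yes, if it is the date of being declared lost (protocol 7.3), of withdrawal through Sponsor termination (protocol 7.2), or of the study-level end (SAP 3.1 and Table 1: 18 months after the last enrolled participant's first dose, or Sponsor stop). No, if the form records the last contact or a consent withdrawal made in contact with the site. The documents do not say which.

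**4. Illustrative size.** All rates here are assumptions. For each median, 400,000 exponential survival times were drawn. Closure was uniform at 18 to 30 months after first dose (18 months plus an assumed 12-month accrual). An exponential loss hazard was set so that 5%, 10% or 20% were lost before death or closure. Lost participants were censored at last contact (reference), at the earlier of last contact plus a gap and closure, or at closure. Each cell shows the rise in the 12-month rate (percentage points) / the rise in the median (months).

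| Median OS | Lost | Gap 1 mo | Gap 3 mo | Gap 6 mo | To closure |
|---|---|---|---|---|---|
| 6 | 5% | 0.2 / 0.04 | 0.7 / 0.11 | 1.4 / 0.16 | 2.2 / 0.16 |
| 6 | 10% | 0.5 / 0.08 | 1.5 / 0.22 | 2.9 / 0.34 | 4.5 / 0.34 |
| 6 | 20% | 1.1 / 0.18 | 3.3 / 0.50 | 6.4 / 0.81 | 9.5 / 0.83 |
| 9 | 5% | 0.2 / 0.04 | 0.5 / 0.13 | 1.0 / 0.22 | 1.4 / 0.26 |
| 9 | 10% | 0.4 / 0.09 | 1.1 / 0.26 | 2.0 / 0.47 | 3.0 / 0.57 |
| 9 | 20% | 0.8 / 0.20 | 2.4 / 0.58 | 4.4 / 1.06 | 6.3 / 1.40 |
| 12 | 5% | 0.1 / 0.05 | 0.4 / 0.13 | 0.7 / 0.26 | 1.0 / 0.38 |
| 12 | 10% | 0.3 / 0.10 | 0.8 / 0.29 | 1.5 / 0.54 | 2.1 / 0.84 |
| 12 | 20% | 0.6 / 0.22 | 1.8 / 0.65 | 3.2 / 1.24 | 4.6 / 2.10 |

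With a gap of zero every entry is 0. A 3-month gap is about one survival-contact interval: 12 × 7 / (365.25/12) = 2.8 months.

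**5. Scale.** With 40 participants (one Part C expansion) and ignoring censoring, the 90% half-width for a 12-month rate p is 1.645 × √(p(1 − p)/40). That is 11.3 points at p = 0.25, 12.7 at 0.40 and 13.0 at 0.50.

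**6. Closure on schedule.** The table covers lost participants only. Those kept in 12-weekly contact until the scheduled end have at least 18 months from first dose, so their last contact is at about 18 − 2.8 = 15.2 months or later. Dating them at closure leaves the estimates up to 12 months unchanged. For this group the landmarks are exposed only if the Sponsor stops early.

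**The case against.** The strongest reply is that the governing rule is already right and the list merely serves it. The Note confines the list to analyses before the final one and to participants still on treatment, which excludes those lost in survival follow-up and the final analysis at Sponsor closure. The limit is real, but the sentence after it drops it and the off-treatment list items contradict it. The scope is unclear, and the objection does not remove the problem.

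A second reply is that the field is undefined and sits on an eCRF not available here. This stands. A reader might infer that lost participants are counted as alive to a date when nobody knew it, that the date falls after last contact by construction, and so that OS is biased upward. The documents do not support that: protocol 7.3 says such participants are considered withdrawn but not which date is entered, and protocol 7.1 and 7.2 allow modified follow-up through relatives, physicians or records. Nor is every other list item plainly an alive contact; the end-of-treatment date is also undefined.

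Third, SAP 4.2.8.3 and the matching rule in 3.3.6 refer to the last alive date in the database without citing this list, so the effect on death dates is conditional.

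Fourth, OS is a descriptive secondary endpoint with no hypothesis and no between-cohort comparison, and SAP 4.2.8.4 reports the numbers lost and withdrawn. That limits the consequence. It does not show how far the censoring dates were moved.

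**Conclusion.** The derivation can contradict the censoring rule it is meant to implement. Followed literally, it lets an undefined date override the survival-status date, and any resulting error is upward. Whether this happens depends on what the eCRF field records; if it is always a contact with a living participant, the bias is zero.

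The size cannot be found from the documents. Across the assumed scenarios with a gap, the 12-month rate rises by 0.1 to 9.5 points and the median by 0.04 to 2.10 months. The middle case (median 9 months, 10% lost, 3-month gap) gives 1.1 points and 0.26 months, about one-eleventh of the half-width at that survival level (1.1/12.7). The bias is probably small against sampling error. Only the extreme case, with 20% lost and all carried to closure, approaches the half-width (9.5 against 11.3). It is worth correcting because the error has one direction and is cheap to avoid.

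**What to change.** In SAP 4.2.8.2, allow the end-of-study date only when the recorded end-of-study reason documents contact with a living participant on that date, for example withdrawal of consent. For loss to follow-up, Sponsor closure or any other administrative end of study, exclude it and censor at the latest remaining date of documented alive status. State that the rule applies to all participants, on and off treatment, and to every OS analysis including the final one. In 4.2.8.3 and 3.3.6, say whether the last-known-alive date comes from the same derivation.

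Deleting the item outright is tempting but would discard a genuine alive date for someone who withdraws consent in contact with the site.

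The cost is one extra condition in the derivation. OS may look slightly less favourable.

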#### 4.2.8.3 Handling of dropouts and missing data

If a participant is known to have died where only a partial death date is available, then the date of death is imputed as the latest of the last date known to be alive +1 from the database and the death date using the available information provided:

- For Missing day only – using the 1st of the month.
- For Missing day and Month – using the 1st of January.

If there is evidence of death but the date is entirely missing, it is treated as missing, i.e. censored at the last known alive date.

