#### 4.2.8.4 Primary Analysis of Secondary Endpoint

The analysis of OS is based on the safety population. The number and percentage of participants experiencing an OS event and Kaplan-Meier plots of OS are presented. The median OS and two-sided 90% CI are estimated using the Kaplan-Meier method if participant numbers allow. Summaries of the number and percentage of participants who have died, those still in survival follow-up, those lost to follow-up and those who have withdrawn consent are provided.

The proportion of participants alive at 3, 6, 9 and 12 months (OS-3, OS-6, OS-9, and OS-12) and associated two-sided 90% CI are estimated using the Kaplan-Meier method.

A summary of the duration of follow-up for OS is included using median (range). This is presented separately for censored and non-censored participants.

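### A death with no date at all is censored in the OS analysis, although the plan elsewhere censors only participants not known to have died

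*SAP*

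**What the plan says.** Three statements in the SAP and one in the protocol bear on this.

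- **Event.** SAP 4.2.8.1 defines OS as "time from the date of first IP dose until death due to any cause".
- **Who is censored.** SAP 4.2.8.2: "Any participant not known to have died at the time of analysis is censored". Protocol 9.4.3 has the same rule: "Any participant not known to have died at the time of analysis will be censored".
- **Partly dated death.** SAP 4.2.8.3 keeps it as an event. The date is "imputed as the latest of the last date known to be alive +1 from the database" and the date built from whatever is known (first of the month, or 1 January).
- **Wholly undated death.** Where there is evidence of death but no part of the date is known, the last sentence of SAP 4.2.8.3 says of the date: "it is treated as missing, i.e. censored at the last known alive date".

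SAP 3.3.6 deals with partial death dates and refers to 4.2.8.3 for detail. SAP 4.2.8.5 plans no sensitivity analysis for OS. SAP section 2, which lists departures from the protocol's planned analyses, does not mention this rule.

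**The concern.** A participant with evidence of death does not clearly belong to the group that SAP 4.2.8.2 and Protocol 9.4.3 allow to be censored, so the plan gives two answers for the same person.

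The treatment also changes abruptly with very little information. If only the year of death is known, and 1 January of that year falls before the last contact, the death is an event on the day after last known alive. Remove the year, and the same participant becomes a non-event. In that example the year contributes nothing to the date used, so the SAP already accepts last known alive plus one day as a workable death date.

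Censoring that happens because the participant died is informative. It lifts the Kaplan-Meier curve from the true death time onward. It would also put a gap between two counts that SAP 4.2.8.4 reports together, OS events and participants who have died, and would place that person in the censored group of the follow-up summary.

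**Working it through.** The documents state no OS event count, assumed survival or OS precision, so there is no figure of the plan's own to reproduce. The check is on direction and size.

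**Inputs from the documents:** Kaplan-Meier estimation with two-sided 90% CI (SAP 4.2.8.4); up to 40 participants per efficacy expansion (Protocol 10.9.2); about 10 per tumour type and dose level in Part B, and 3 to 9 per dose level in Part A (Protocol 10.9.2); survival contact about every 12 weeks (Protocol 8.2.8).

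**Assumptions, not in the documents:** exponential OS with median 6, 9 or 12 months; for the simulation, 2.5%, 5% or 10% of deaths undated, follow-up of 18 to 30 months, and a gap from last known alive to death that is uniform over 0 to 12 weeks.

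**One undated death.** Take n participants with no other censoring before time t. Let r be the number at risk at the undated participant's last known alive date, including that participant, and s the number alive at t, after the true death.

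- True curve: S(t) = s/n.
- SAP rule: (r/n) × s/(r − 1) = S(t) × r/(r − 1).

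With n = 40 and death times spread evenly over the exponential quantiles, for an early and a later undated death:

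| Median (months) | True OS-12 | r | SAP rule | Rise (points) |
|---|---|---|---|---|
| 6 | 0.250 | 40 | 0.250 × 40/39 = 0.256 | 0.6 |
| 6 | 0.250 | 34 | 0.250 × 34/33 = 0.258 | 0.8 |
| 9 | 0.400 | 40 | 0.400 × 40/39 = 0.410 | 1.0 |
| 9 | 0.400 | 30 | 0.400 × 30/29 = 0.414 | 1.4 |
| 12 | 0.500 | 40 | 0.500 × 40/39 = 0.513 | 1.3 |
| 12 | 0.500 | 29 | 0.500 × 29/28 = 0.518 | 1.8 |

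Between last known alive and the true death the curve is slightly low, because the risk set has lost someone still alive. For the 9-month case with r = 30 and 25 still alive, the SAP rule gives (30/40) × (24/29) = 0.621 against a true 25/40 = 0.625. The lift starts at the true death.

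**Small cells.** In a Part B cell of 10 with r = 10, the factor is 10/9, an 11.1% relative rise; with 4 of 10 alive at 12 months, 0.400 becomes 0.444. In a Part A cohort of 9 it is 9/8, or 12.5%.

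**A share m of deaths undated.** If the censoring falls close to death, the event hazard is multiplied by (1 − m). Kaplan-Meier then estimates S(t)^(1 − m), and the exponential median is multiplied by 1/(1 − m): 1.026, 1.053 and 1.111 for m = 2.5%, 5% and 10%. For a 9-month median, OS-12 moves from 0.397 to 0.406, 0.416 and 0.435.

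A simulation (4,000 runs, n = 40, true median 9 months) agrees and also tests an event at last known alive + 1 day:

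| m | OS-12 true | SAP rule | Event at +1 day | Median true | SAP rule | Event at +1 day |
|---|---|---|---|---|---|---|
| 2.5% | 0.397 | 0.406 | 0.396 | 8.83 | 9.18 | 8.80 |
| 5% | 0.395 | 0.412 | 0.393 | 8.80 | 9.45 | 8.75 |
| 10% | 0.399 | 0.433 | 0.395 | 8.89 | 10.11 | 8.77 |

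At true medians of 6 and 12 months the SAP rule raises OS-12 by 0.7 to 3.1 and 0.8 to 3.3 points respectively. The average bias is upward in every scenario.

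**The case against.** The best defence has four parts.

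- **The wording is weaker for undated deaths.** SAP 4.2.8.3 speaks of participants known to have died when the date is partial, but only of evidence of death when it is wholly missing. A reader might infer that the plan censors deaths that are certain; the text does not say that. This stands, and the fix should be limited to confirmed deaths. It does not rescue the rule, because the SAP never separates confirmed from suspected deaths and so censors both.
- **There is a general review route.** SAP 3.3.6 says wholly missing dates are reviewed within the study, and warns against using imputed dates for durations where that is less accurate. But 4.2.8.3 is the specific OS instruction and is not overridden by general guidance. The partial-date rule beside it already uses an imputed date in the OS duration.
- **It may never happen.** Date of death is a collected variable for SAEs (Protocol 8.3.2), deaths are documented in the eCRF (Protocol 8.3.12), and survival contact is regular. This stands: the number of cases is unknown, probably small, and may be zero. Late follow-up can, however, rest on telephone calls, relatives or records (Protocol 7.1 and 8.2.8), and the SAP authors thought the case worth a rule.
- **Little depends on it.** OS is secondary, there is no hypothesis (Protocol 10.9.1) and no comparison between cohorts (Protocol 10.9.4.1). At survival 0.40 with n = 40, an approximate 90% half-width is 1.645 × √(0.40 × 0.60/40) = 0.127, about 13 points, against a shift of 1 to 1.4 points from one undated death. This stands and sets the severity.

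**Conclusion.** The contradiction is real and confined to OS. Followed as written, SAP 4.2.8.3 turns a death into a non-event, against SAP 4.2.8.2, Protocol 9.4.3 and the logic of its own partial-date rule. For one undated death among 40, OS-12 rises by about 0.6 to 1.8 points under the assumed exponential medians of 6 to 12 months. The relative effect is larger in Part A and Part B cells, where the estimates are very imprecise anyway. If the participant is tabulated as dead, the OS event count and the number who died differ by one for each case. That mismatch is conditional on a case occurring and would be visible in the same output. No type I error or power is involved. This is a minor point, worth making because it is cheap to correct.

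A reader might infer that PFS is overstated as well. The documents do not show this. PFS has its own derivation and censoring table (SAP 4.2.6.2, Table 9), with censoring at the last evaluable disease assessment; it does not invoke the OS rule and gives no rule for an undated death. The calculations here cover OS only.

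**What to change.** Replace the last sentence of SAP 4.2.8.3 with a rule along these lines: where death is confirmed but the date is wholly missing, the participant has an OS event on the last known alive date plus one day; the imputation is flagged in the listing, and the number of such participants is reported with the OS summary. State what counts as confirmation, and leave participants with unconfirmed evidence of death under the ordinary censoring rule. Optionally show OS with these deaths censored as a check.

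The cost is one or two SAP sentences and a flag. The downside is that OS becomes slightly less favourable. The day after last known alive is the earliest possible date, so a small conservative bias remains. With a 9-month median and 10% of deaths undated, the simulated OS-12 was 0.4 points below truth and the median about 0.13 months below (8.765 against 8.894). At 3 months the shortfall was 0.8 points (0.787 against 0.795), compared with an excess of 1.7 points under the present rule (0.812).
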